3 PATIENT SELECTION

3.1 Eligibility Criteria

- 3.1.1 ScGVHD manifesting after at least 100 days following allogeneic hematopoietic stem cell transplantation is considered diagnostic for cGVHD according to NIH cGVHD Consensus Statement diagnostic criteria [10,13]. The diagnosis can be made clinically or by histopathology. The diagnosis must be confirmed by the principal investigator (PI), or lead associate investigator (LAI). Skin biopsies will be reviewed by the NCI Laboratory of Pathology to confirm the diagnosis of ScGVHD.
- 3.1.2 Patients must have measurable limitation in range of motion, defined as ScGVHD with or without fasciitis, restricting range of motion (ROM) of at least one joint with a minimum deficit of 25%. See Section 11 for the evaluation of measurable disease.
- 3.1.3 Prior therapy: Patients must have cGVHD refractory to at least one treatment regimen for cGVHD. One prior regimen must have included systemic corticosteroids at the equivalent prednisone dosing of 1mg/kg/day x 14 days. Patients in whom calcineurin inhibitors or

corticosteroids are medically contraindicated may also be eligible for enrollment. Patients who have had stabilization of disease on calcineurin inhibitors or steroids, but in whom these medications cannot be tapered without disease flare are also eligible. Patient must be on stable or tapering immunosuppressive regimen for at least one month.

- 3.1.4 Age: 4 years of age or older at the time of enrollment. Lower age limit set by lower established age limit norms of ROM scores for measurement criteria.
- 3.1.5 Life expectancy of greater than 6 months.
- 3.1.6 Karnofsky $\geq 60\%$; see Appendix A.
- 3.1.7 Patients must be platelet transfusion and growth factor independent at the time of study entry. Patients must have adequate organ and marrow function as defined below. Patients with Gilbert syndrome are excluded from the requirement of a normal bilirubin. (Gilbert syndrome is found in 3-10% of the general population, and is characterized by mild, chronic unconjugated hyperbilirubinemia in the absence of liver disease or overt hemolysis).

- X absolute neutrophil count $\geq 1,000/\text{mcL}$
- X platelets $\geq 50,000/\text{mcL}$
- X total bilirubin $< 3x$ upper limit of normal
- X AST(SGOT)/ALT(SGPT) $< 5 x$ upper limit of normal
- X creatinine age-adjusted within normal limits

OR

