Hematology 3 Platelet count 4 Eosinophil count 5 ≥ 3 X ULN • < 3 X ULN	$s - e \geq 50,000/\mu\text{L}$ and $e < \text{LLN}$ $e - s \geq 3$ X ULN $e - s \geq 2$ X ULN
Gastrointestinal (0 -3 scales)	$e - s \geq 1$
Liver function (ALT, alkaline phosphatase and bilirubin) 6 $s \geq 3$ X ULN 7 $s < 3$ X ULN	$e - s \geq 3$ X ULN $e - s \geq 2$ X ULN
Lungs (Lung function scale 12 points)²	$e - s \geq 3$
Other	> 1 steroid pulse per 3 month period

Abbreviation: s: starting score or value; e: ending score or value; ULN: upper limit of normal; LLN: lower limit of normal. If the starting lung function score is ≥ 10 , progression is defined as $\geq 5\%$ decrease of FEV₁ in two tests measured at least 2 weeks apart.

Partial Response (PR): defined as at least one of the following:

Organ and Starting Score or Value at Baseline	Partial Response Criterion¹
Skin (% of BSA) 8 > 50 9 25-50 10 < 25	$e/s \leq 0.5$ and $e > 0$ $s - e \geq 25$ and $e > 0$ Only CR; no PR possible
Eye (mm Schirmer's test) 11 < 5 mm 12 5-10 mm	$e - s \geq 5$ mm and $e < \text{LLN}$ Only CR; no PR possible
Mouth (Schubert Scale 0-15) 13 > 8 14 4-7 15 < 4	$e/s \leq 0.5$ and $e > 0$ $s - e \geq 4$ and $e > 0$ Only CR; no PR possible
Hematology 16 Platelet count 17 Eosinophil count 18 $\geq 3 \times \text{ULN}$ 19 $< 3 \times \text{ULN}$	$e - s \geq 100,000/\mu\text{L}$ and $e < \text{LLN}$ $e/s \leq 0.5$ and $e > \text{ULN}$ Only CR; no PR possible
Gastrointestinal (0 -3 scales) 20 3 21 2 22 1	$e = 1$ or 2 $e = 1$ Only CR; no PR possible
Liver function (ALT, alkaline phosphatase and bilirubin) 23 $\geq 3 \times \text{ULN}$ 24 $< 3 \times \text{ULN}$	$e/s \leq 0.5$ and $e > \text{ULN}$ Only CR; no PR possible
Other	Stable disease in the face of weaning steroid.

Abbreviations. s: starting score or value; e: ending score or value; ULN: upper limit of normal; LLN: lower limit of normal

Complete Response (CR): defined as at least one of the following

1. Skin: >90% reduction of baseline involvement.
2. Ophthalmologic: Return to normal Schirmer's score in both eyes.
3. Oral: Resolution of oral mucosal involvement.
4. BO: PFT: improvement in FEV1 > 0.70.
5. Liver: Normalization of laboratory values of transaminases and bilirubin.
6. GI: (Upper GI) Absence of symptoms of nausea, dysphagia, vomiting, and odynophagia and stable weight. (Lower GI) Absence of diarrhea and stable weight.

32 Appendix Q: Patient Instructions

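### Appendix P defines no hematologic complete response, so normalized platelets or eosinophils are never scored as a response, and platelet partial response is unattainable from the eligible range if LLN is 150,000/uL or lower

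*Combined protocol and SAP*

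**What the plan says.** Section 12.1 sends the evaluation of organs other than sclerotic skin to Appendix P and keeps it out of the primary response. Appendix P then gives three sets of rules, with s the starting and e the ending value.

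- **Progression.** Both counts have rules. For platelets: "s - e \geq 50,000/\mu\text{L}$ and $e < \text{LLN", a fall of at least 50,000/uL to below LLN.
- **Partial response.** For platelets: "e - s \geq 100,000/\mu\text{L}$ and $e < \text{LLN". For eosinophils starting at 3 x ULN or more: "e/s \leq 0.5$ and $e > \text{ULN", at least halved but still above normal. For eosinophils starting below 3 x ULN: "Only CR; no PR possible".
- **Complete response.** The list opens "Complete Response (CR): defined as at least one of the following" and has six items: skin, eye, mouth, bronchiolitis obliterans, liver and GI. None concerns blood counts.

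The table note expands the abbreviation ("LLN: lower limit of normal") but gives no number. On the starting range, section 3.1.7 requires "platelets $\geq 50,000/\text{mcL" per microliter and adds: "Patients must be platelet transfusion and growth factor independent at the time of study entry".

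**The concern.** A PR rule that stops short of normal is sensible only if a CR rule takes over at normal. For blood counts nothing takes over. The scoring then runs backwards: an eosinophil count that halves but stays high is a response, while one that returns to normal is not. The eosinophil row for lower starts refers to a CR definition that does not exist.

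The platelet row has a second difficulty. A required rise of 100,000/uL that must still end below normal needs a very low start, and the eligibility floor removes most or all such starts.

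Progression on both counts remains attainable, so the hematology rows are tilted towards recording harm. This matters somewhat for this drug. Section 5.2.4 describes thrombocytopenia as regularly seen with imatinib, and section 2.3 cites its approval in eosinophilic disorders. Movement in both counts is therefore plausible. At stake is the secondary objective on the response of other organ manifestations (section 1.2).

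**Working it through.** The plan gives no figure to reproduce here. The check is whether the stated inequalities can be met.

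**Inputs.** Platelet PR (Appendix P): e - s >= 100,000 and e < LLN. Platelet floor (section 3.1.7): s >= 50,000. LLN: not given, so 130,000 to 200,000/uL is tried as an assumption. It is also assumed that the baseline count used for scoring still meets the entry floor.

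**Platelet PR.** Combining the two conditions gives s + 100,000 <= e < LLN, so s < LLN - 100,000. With s >= 50,000, the smallest qualifying end value is 50,000 + 100,000 = 150,000. PR therefore requires LLN > 150,000.

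| Assumed LLN (/uL) | Eligible starts that can reach PR | Share of the range from 50,000 to LLN |
|---|---|---|
| 130,000, 140,000, 150,000 | none | 0% |
| 160,000 | 50,000 to <60,000 | 10,000/110,000 = 9.1% |
| 170,000 | 50,000 to <70,000 | 20,000/120,000 = 16.7% |
| 180,000 | 50,000 to <80,000 | 30,000/130,000 = 23.1% |
| 200,000 | 50,000 to <100,000 | 50,000/150,000 = 33.3% |

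The last column is a share of the numerical range, not of patients; the documents give no distribution of baseline counts.

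**Normalization of platelets.** Normal means e >= LLN, which contradicts e < LLN whatever the LLN is. With LLN at 150,000, a rise from 60,000 to 200,000 is 140,000, well over the threshold, yet it fails PR because 200,000 is not below LLN. No CR item picks it up.

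**Eosinophils, in multiples of ULN.**
- 3.0 to 1.5: ratio 0.5, still above 1, so PR.
- 3.0 to 1.0: ratio 0.33, not above 1, so neither PR nor CR.
- 2.9 to 0.9: PR is ruled out by the row and no CR exists, so no response.

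**Comparison with other rows.** The CR-only label also appears for low starting values of skin, eye, mouth, GI and liver. Each of those five has a CR item. Eosinophils are the only row with the label and no CR item. Liver has the same PR form as eosinophils, and its CR item covers normalization.

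**Progression.** With LLN at 150,000, a platelet fall from 150,000 to 90,000 is 60,000, at least 50,000, and ends below LLN. The rule can be met.

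**The case against.** The strongest reply is that hematology was never meant to be a scored organ. Appendix P opens with a numbered list of six manifestations, and the CR list covers the same six. Section 14.4 names no hematologic response rate, and PR and CR are each met by any one organ, so no separate hematologic rate is prescribed. On this view the hematology rows are an editorial leftover. That may well be so, but the rows are still there, they can label a patient as progressed or partially responding, and one of them refers to a missing definition. The reply supports removing the rows; it does not make them work.

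It is also fair that a PR rule stopping short of normal is not itself an error. Other rows do the same to separate PR from CR. The fault is the absent CR item.

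Three stronger readings are tempting, and the documents do not support them:
- *No eligible patient can ever meet platelet PR.* This holds only if LLN is 150,000/uL or lower, and no LLN is stated.
- *The hematologic response rate is close to zero by construction.* Eosinophil PR can be reached from starts of 3 x ULN or more, and baseline counts are unknown.
- *The objective cannot be answered for blood counts.* Appendix H records the counts as numbers, Appendix B schedules blood counts with differential throughout, and section 14.4 treats secondary endpoints as exploratory. Changes can be described without a response label.

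Finally, the PR column heading carries a footnote mark whose text is not in the available copy, and section 2.2 bases response assessment on external consensus criteria that cannot be consulted here. Either might qualify the table. Neither would put a hematology item in the CR list as printed.

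**Conclusion.** The point holds in limited form. Three parts need no assumption about LLN: no hematologic CR is defined, full normalization of either count is never scored as a response, and eosinophil starts below 3 x ULN have no count-based response category. The Appendix P row that credits stable disease during steroid weaning could still yield a PR, but it does not score counts.

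The platelet PR result is conditional: impossible for eligible starts if LLN is 150,000/uL or lower, and otherwise possible only from 50,000 to just under LLN - 100,000. It rests on the baseline count respecting the entry floor.

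Severity is minor. Section 12.1 keeps these organs out of the primary response, and range of motion, tolerability and the toxicity stopping rule do not use these rows. Because CR and PR are each met by any one organ, a patient's overall category changes only when the count would have decided it.

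**What to change.** Choose one of two routes before secondary response is tabulated.

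1. **Keep hematology as a scored manifestation.** Add a CR item: platelets at or above LLN for patients starting below LLN, and eosinophils at or below ULN for patients starting above ULN. The restriction on starting values is needed because CR is met by any one item; without it, every patient with normal counts throughout would qualify. Then reconcile the platelet PR threshold with the eligible starting range, or mark platelets as CR-only, as is done elsewhere in the table. If a new platelet PR rule is written, it should not reward small rises near normal. For example, recovery of half the shortfall with no minimum rise would, at an LLN of 150,000, count 140,000 to 145,000 as a response. State the LLN and ULN to be used.
2. **Treat hematology as unscored.** Remove its rows from the progression and PR tables and report platelet and eosinophil counts descriptively.

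Either route is a wording change in Appendix P. The counts are already collected, so no new data, visits or patients are needed. If accrual has ended, a dated clarification before tabulation is enough.

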GI TRACT	 No symptoms	 Symptoms such as dysphagia, anorexia, nausea, vomiting, abdominal pain or diarrhea without significant weight loss (<5%)	 Symptoms associated with mild to moderate weight loss (5-15%)	 Symptoms associated with significant weight loss >15%, requires nutritional supplement for most calorie needs OR esophageal dilation
LIVER	 Normal LFT	 Elevated Bilirubin, AP*, AST or ALT <2 x ULN	 Bilirubin >3 mg/dl or Bilirubin, enzymes 2-5 x ULN	 Bilirubin or enzymes > 5 x ULN
LUNGS*	 No symptoms	 Mild symptoms (shortness of breath after climbing one flight of steps)	 Moderate symptoms (shortness of breath after walking on flat ground)	 Severe symptoms (shortness of breath at rest; requiring O ₂)
FEV1 				
DLCO 	 FEV1 > 80% OR LFS=2	 FEV1 60-79% OR LFS 3-5	 FEV1 40-59% OR LFS 6-9	 FEV1 <39% OR LFS 10-12
JOINTS AND FASCIA	 No symptoms	 Mild tightness of arms or legs, normal or mild decreased range of motion (ROM) AND not affecting ADL	 Tightness of arms or legs OR joint contractures, erythema due to fasciitis, moderate decrease ROM AND mild to moderate limitation of ADL	 Contractures WITH significant decrease of ROM AND significant limitation of ADL (unable to tie shoes, button shirts, dress self etc.)
GENITAL TRACT	 No symptoms	 Symptomatic with mild signs on exam AND no effect on coitus and minimal discomfort with gynecologic exam	 Symptomatic with moderate signs on exam AND with mild dyspareunia or discomfort with gynecologic exam	 Symptomatic WITH advanced signs (stricture, labial agglutination or severe ulceration) AND severe pain with coitus or inability to insert vaginal speculum

* AP may be elevated in growing children, and not reflective of liver dysfunction

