Other indicators, clinical manifestations or complications related to cGVHD (check all that apply and assign a score to its severity (0-3) based on its functional impact (none – 0, mild -1, moderate -2, severe – 3)

- | | | |
|-----------------------------------|----------------------------------|-----------------------------------|
| ↑ Esophageal stricture or web ___ | ↑ Pericardial Effusion ___ | ↑ Pleural Effusion(s) ___ |
| ↑ Ascites (serositis) ___ | ↑ Nephrotic syndrome ___ | ↑ Peripheral Neuropathy ___ |
| ↑ Myasthenia Gravis ___ | ↑ Cardiomyopathy ___ | ↑ Eosinophilia > 500µl ___ |
| ↑ Polymyositis ___ | ↑ Cardiac conduction defects ___ | ↑ Coronary artery involvement ___ |
| ↑ Platelets <100,000/µl ___ | ↑ Progressive onset | |
| ↑ OTHERS: _____ | | |

23 Appendix H: Chronic GVHD Manifestations

Component	Items assessed	Measure	Assessor*
Skin	Erythematous and/or papular rash of any sort	% body surface area	C
	Superficial sclerosis (movable)	("rules of 9's")	C
	Deep sclerosis (non-moveable)		C
	Ulcers	largest dimension (cm) of the largest ulcer	C
	Pruritus or itching	0 – 10 scale	P
Eyes	Bilateral Schirmer's tear test scores without anesthesia	Mean of both eyes (mm)	C
	Chief ocular complaint at the time of the visit	0 – 10 scale	P
Mouth	Erythema	Total score 0 – 15	C
	Lichen-type Hyperkeratosis		C
	Ulcerations		C
	Mucoceles		C
	Symptoms of oral pain, dryness, sensitivity	0 – 10 scale	P
Hematology	Platelet count, eosinophils	number/ μ L	C
Gastrointestinal	Upper GI symptoms	0 – 3 score	C/P
	Esophageal symptoms	0 – 3 «	C/P
	Diarrhea	0 – 2 «	C/P
Liver	total serum bilirubin	mg/dL	C
	ALT, alkaline phosphatase	U/L	C
Lungs	Bronchiolitis obliterans syndrome	FEV1, DLCO	C
Chronic GVHD Symptom scale ^[37]	30 items, 7 subscales, 1 summary scale	1-100	P
Global activity rating	Severity of chronic GVHD symptoms	0 – 10	C/P
	Perception of change	+3 to -3	C/P
	Overall severity of chronic GVHD	Mild – Moderate-Severe	C/P

- Vulvar-vaginal symptoms (yes or no) and patient weight should be recorded at each visit. Range of motion of the most affected joints should be recorded, depending on the availability of a physical therapist.

*C=assessed by the clinician; P=reported by the patient

24 Appendix I: Core set of measures for assessing responses in chronic GVHD trials

Measure	Clinician Assessed	Patient Reported
I. Chronic GVHD specific measures		
Signs	Organ specific measures	N/A

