	Trial 1	Trial 2	Trial 3	Average	% of Predicted
R					
L					

4) Walk Velocity:

Total Distance Walked in 2 Minutes _____ feet walked in 2 minutes, giving him/her velocity _____. % of predicted _____

5) HAP: _____ AAS _____

Version date: 04/20/15

MRN:

AAROM:

Cervical spine:

Flexion	Extension	R SB	L SB	R Rotation	L Rotation

Shoulders:

	Abduction	Flexion	IR	ER
R				
L				

Elbows:

	Extension	Flexion
R		
L		

Wrists:

	Extension	Flexion
R		
L		

Hips:

	IR	ER
R		
L		

Knees:

	Extension	Flexion
R		
L		

Ankles:

	ADF	APF
R		
L		

Signature

Printed Name

Date

30 Appendix O: Lung Function Score

The Lung function score (LFS) is computed by the extent of FEV₁ and DLCO compromise (>80% = 1, 70 – 79% = 2, 60 – 69% = 3, 50 – 59% = 4, 40 – 49% = 5, <40% = 6). The scores for FEV₁ and DLCO are then added together, and the sum is reduced to an overall category according to the following table.

Category	30.1.1 Lung function	30.1.2 LF score
I	Normal	2
II	Mild decrease	3 – 5
III	Moderate decrease	6 – 9
IV	Severe decrease	10 – 12

It is important to emphasize that LFS has never been used in chronic GVHD response assessments and its exact role in this setting needs to be determined. To allow validation in trials absolute values of both FEV₁ and DLCO are recorded on the data collection forms.

31 Appendix P: Scoring of non-ScGVHD cGVHD manifestations

1. Skin GVHD (Dermatology): Total skin score (Appendix E)
2. Oral GVHD (Dental): Total mouth score (Appendix E)
3. Ophthalmologic GVHD (Ophthalmology): Response based on determination of bilateral Schirmer's Test (without topical anesthesia >9 y/o, with topical anesthesia <9 years old.)
4. Bronchiolitis obliterans (PFTs): Measure of absolute FEV1 and lung function score (Appendix O). BO response will be measured by standard pulmonary function tests. Patients will be evaluated by complete PFT's (with and without bronchodilators) and baseline will be the best measured FEV1. Percent change is based on the relative change as compared to baseline. PFT testing variability is typically <10% and a 20% change is thought to be significant.
5. Liver GVHD: Laboratory values: ALT, AST, total bilirubin, alkaline phosphatase.
6. Gastrointestinal GVHD: Gastrointestinal symptom score (Appendix E).

Progression (PD): defined as at least one of the following:

Organ and Starting Score or Value	Progression Criterion
Skin (% of BSA)	$e - s \geq 25$
Eye (mm Schirmer's test)	$s - e \geq 5$ mm
Mouth (Schubert Scale 0-15)	$e - s \geq 3$

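### Liver complete response in Appendix P leaves out alkaline phosphatase, so when transaminases and bilirubin normalise an unresolved liver can be scored CR, or CR together with PR or progression

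*Combined protocol and SAP*

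**What the plan says.** All the liver rules are in Appendix P, the scoring of manifestations other than sclerotic skin disease.

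- **Measures list, item 5:** "Liver GVHD: Laboratory values: ALT, AST, total bilirubin, alkaline phosphatase".
- **Progression and partial response tables:** both liver rows carry the label "Liver function (ALT, alkaline phosphatase and bilirubin". AST is not in it.
- **Complete response list, item 5:** "Liver: Normalization of laboratory values of transaminases and bilirubin". Alkaline phosphatase (ALP) is not mentioned.
- **How items combine:** "Progression (PD): defined as at least one of the following"; "Partial Response (PR): defined as at least one of the following"; "Complete Response (CR): defined as at least one of the following". Nothing says what to do when one patient meets two categories.

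Elsewhere ALP is treated as a liver measure. Appendix H lists "ALT, alkaline phosphatase" under liver, the Appendix E activity form has a field for it, and Appendix G counts it in the liver score. The one caveat is a footnote to Appendix G: "AP may be elevated in growing children, and not reflective of liver dysfunction".

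Section 1.2 makes the response of other organs a secondary objective. Section 12.1 keeps those organs out of the scoring of response to therapy, and Section 14.4 treats every secondary endpoint as exploratory.

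**The concern.** A complete response should mean that every measure used to judge the organ has resolved. Here one of the four declared measures can establish a partial response or progression but cannot prevent a complete response. For a patient whose liver involvement shows mainly in ALP, the best category may be awarded while the main abnormality is unchanged or worse. In other patterns the same liver meets two categories at once, and whoever tabulates the data must choose between them without guidance. A reader of a published liver CR count would take the word complete at face value.

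**Working it through.** The documents give no figure to reproduce, so the check applies the rules as written to assumed patients.

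**Rules** (s = start, e = end, in multiples of ULN)

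- Progression, for ALT, ALP or bilirubin: e − s ≥ 3 if s ≥ 3; e − s ≥ 2 if s < 3.
- PR, for the same three tests: e/s ≤ 0.5 and e > 1 if s ≥ 3; no PR is available if s < 3.
- CR as written: ALT, AST and bilirubin normal at the end (e ≤ 1), with at least one of them abnormal at the start. The second part is my reading of normalisation.
- CR as proposed: ALT, AST, bilirubin and ALP all ≤ 1 at the end, with at least one abnormal at the start.

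**Assumed patient.** ALT and AST start at 3, bilirubin at 1.5, and all three end at 0.9. These starting values are within the limits in Section 3.1.7 (AST/ALT below 5, bilirubin below 3), which sets no limit on ALP. ALT gives no PR because it ends below ULN. Only ALP varies.

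| ALP start → end | Arithmetic | As written | CR with ALP added? |
|---|---|---|---|
| 6 → 6 | rise 0; ratio 1 | CR | No |
| 2.5 → 2.5 | rise 0; s < 3 | CR | No |
| 2.5 → 4 | rise 1.5 < 2 | CR | No |
| 0.9 → 2.5 | rise 1.6 < 2 | CR | No |
| 6 → 2.5 | 2.5/6 = 0.42 ≤ 0.5; 2.5 > 1 | CR and PR | No |
| 4 → 2 | 2/4 = 0.5; 2 > 1 | CR and PR | No |
| 2.5 → 4.5 | rise 2.0 ≥ 2 | CR and progression | No |
| 4 → 7 | rise 3 ≥ 3 | CR and progression | No |
| 4 → 1 | normal at end | CR | Yes |
| 1 → 1 | normal throughout | CR | Yes |

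**ALP as the only abnormality.** If ALP goes from 2.5 to 0.9 with the other tests normal throughout, the liver fits no category as written. PR is closed below 3 x ULN, and the CR rule has no abnormal value to normalise. With ALP added it is a CR.

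**Cross-check with Appendix G.** The worst liver score, 3, is given for bilirubin or enzymes above 5 x ULN. The score-1 cell names AP alongside AST and ALT, so enzymes appears to include it. On that reading the 6 → 6 patient scores 3 in Appendix G and CR in Appendix P at the same visit.

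**Why precedence is still needed after the change.** With all four tests required to be normal, liver CR can no longer coincide with liver PR (some test above ULN) or liver progression (a rise of at least 2 x ULN ends above ULN). PR and progression can still coincide: ALT 4 → 2 is PR (2/4 = 0.5, 2 > 1), while ALP 2.5 → 4.5 in the same patient is progression.

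**The case against.** **Impact is low.** Organ responses are not used in scoring response to therapy and are exploratory. The primary endpoint, sample size, tolerability rule and stopping rule do not depend on them. This stands, and it limits how much weight the point deserves.

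**The omission may be deliberate.** The trial enrols from age 4, and Appendix G warns that ALP can be raised in growing children. But that footnote is not attached to the CR rule, does not apply to adults, and does not explain keeping ALP for PR and progression while dropping it for CR. Drug effect does not explain it either: the list in Section 8.1 gives increases in ALT, AST and bilirubin as possibly related to imatinib as well as ALP, and CR keeps the first three.

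**Stronger readings go too far.** A reader might infer any of the following; the documents do not support them.

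- *Any patient with persistently raised ALP is a liver CR.* This holds only if ALT, AST and bilirubin all normalise, and a large enough ALP rise also meets progression.
- *CR is easier to reach than PR.* Not in general: ALT 4 → 2 x ULN is PR and not CR. The inversion is confined to patterns led by ALP. CR without an available PR is also a regular feature of these tables at low starting values.
- *Each case moves the liver CR rate by 10 points.* That assumes a denominator of 10 (1/10). No liver CR rate is defined, and Section 14.4 uses however many patients supply the data.
- *Patients with high ALP are automatically eligible.* Section 3.1.7 sets no ALP limit, but Section 3.2.7 separately excludes some uncontrolled hepatic dysfunction.
- *ALP is not measured on study.* Sections 11.1.2 and 11.1.3 do not name it, but Appendix B schedules a Chem 20 panel on study and after it. The panel's contents are not listed, so the gap is possible, not shown.

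**Conclusion.** The mismatch is in the text, and nothing in the documents explains or resolves it. When transaminases and bilirubin normalise, the rule as written gives a liver CR to a patient whose ALP stays high or rises modestly. It gives CR with PR when ALP halves from at least 3 x ULN but remains above ULN, and CR with progression when ALP rises by at least 2 x ULN (start below 3) or 3 x ULN (start 3 or more). No precedence rule settles these overlaps.

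The effect is confined to the exploratory organ-response endpoint. Its numerical size cannot be stated, because the documents give neither the number of patients with liver involvement nor the share with raised ALP. The laboratory values above are assumed; the classifications follow from the rules once those values are set. The point is worth correcting because it is cheap, but the trial's main conclusions do not depend on it.

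**What to change.** 1. Reword CR item 5 to require at least one liver test abnormal at baseline, and ALT, AST, total bilirubin and ALP all within normal limits at assessment, with an age-adjusted ALP limit in growing children. The condition must cover all four tests, not just those abnormal at baseline; otherwise a newly raised ALP (0.9 → 2.5 x ULN) would remain a CR.
2. Use one set of analytes in the CR, PR and progression rules. AST is in the measures list and, as a transaminase, in CR, but is missing from the PR and progression rows.
3. State that progression takes precedence over response.
4. Name ALP in the chemistry lists of Sections 11.1.2 and 11.1.3, or confirm that the Appendix B Chem 20 panel includes it. The Section 11.1.3 list also lacks AST, so check both there.

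The cost is a few lines in Appendix P, one named laboratory test and slightly fewer liver CRs. The primary analysis and the sample size do not change.
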